7. PHARMACODYNAMICS ANALYSIS

The following sub-sections are organized based on exploratory endpoints 1 to 5 in [Section 2.2](#).

7.1 Biomarkers and Quality of Life Assessments

7.1.1 Measurements, Collection Schedule, and Analysis

7.1.1.1 Biomarkers in Bronchoalveolar Lavage Samples

BAL samples for PD assessments of biomarkers will be collected at baseline at Check-in and on Day 55 or 56 of the Treatment Period.

BAL (lavage material) will be performed in the right middle or lower lobe. BAL cell pellet and supernatant will be kept cooled until processed or stored as indicated in the laboratory manual to be provided as a separate document.

Samples must be protected from UV light during collection, processing, and storage.

Biomarkers assessments in BAL include:

- White blood cell (WBC) count (cells/mL) and differential (including macrophages, lymphocytes, neutrophils, and eosinophils) will be expressed as

raw counts and % change from baseline and as a percent (%) of WBC for each differential.

WBC and differential in BAL will be determined using a differential stain (blood smear; microscopic examination with manual differential WBC count) at the local Investigator sites.

- Concentrations of TNF- α , IL-1 β , IL-4, IL-5, IL-6, IL-8, IL-13, MPO, neutrophil elastase, MCP-1, and MMP-9 will be expressed as raw and % change from baseline levels. Baseline is defined as Check-in of the Treatment Period level and is patient specific.

The concentrations of MPO, neutrophil elastase, MMP-9 will be determined using enzyme-linked immunosorbent assay (ELISA) assays and the rest of BAL inflammatory markers will be determined using Luminex® assays. All assays are validated with respect to accuracy, precision, linearity, sensitivity, and specificity at Temple University School of Medicine (Philadelphia, Pennsylvania, USA).

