7.1.2 Data Summarization and Presentation

Descriptive statistics will be generated using SAS[®] Version 9.3 (or higher) for the actual values (raw) and relative values (% change from baseline or total) as specified above for each type of biomarker variable. When applicable, the PD biomarkers (BAL, blood, pulmonary function) will be summarized by treatment group and time point using descriptive statistics including sample size (N), arithmetic mean, standard deviation (SD), coefficient of variation (CV%), median, minimum, and maximum.

Figures will be created to display mean measure, level or activity value as a function of time on linear plots with and without SD, as appropriate.

The quality of life parameters reported from the BDI/TDI and CAT questionnaires will be listed and presented descriptively using SAS® Version 9.3 (or higher)

Additional analysis may be performed if deemed appropriate.

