14.2.2 Pharmacodynamic Tables

BAL Biomarkers

Table 14.2.2.1 Summary of BAL WBC Counts and Differential Following Multiple Oral YPL-001 Doses of 80 mg and 160 mg and Placebo in COPD Patients (Treatments A - C) (Raw, % Change from Baseline, and % of WBC)

Table 14.2.2.2 Summary of BAL Inflammatory Marker Concentrations Following Multiple Oral YPL 001 Doses of 80 mg and 160 mg and Placebo in COPD Patients (Treatments A - C)

Table 14.2.2.3 Summary of BAL Inflammatory Marker Concentration Changes Following Multiple Oral YPL 001 Doses of 80 mg and 160 mg and Placebo in COPD Patients (Treatments A - C) (Raw and % Change from Baseline)

Blood Biomarkers

Table 14.2.2.4 Summary of Blood WBC Counts and Differential Following Multiple Oral YPL-001 Doses of 80 mg and 160 mg and Placebo in COPD Patients (Treatments A - C) (Raw and % of WBC)

Table 14.2.2.5 Summary of Blood Inflammatory Marker Concentrations
Following Multiple Oral YPL 001 Doses of 80 mg and 160 mg
and Placebo in COPD Patients (Treatments A - C)

Table 14.2.2.6 Summary of Blood Inflammatory Marker Concentration
Changes Following Multiple Oral YPL 001 Doses of 80 mg
and 160 mg and Placebo in COPD Patients (Treatments A - C)
(Raw and % Change from Baseline)

Pulmonary Function Biomarkers

Table 14.2.2.7 Summary of Spirometric Functions Following Multiple Oral
YPL-001 Doses of 80 mg and 160 mg and Placebo in COPD
Patients (Actual Results, Treatments A - C)

Table 14.2.2.8 Summary of Spirometric Functions Following Multiple Oral
YPL-001 Doses of 80 mg and 160 mg and Placebo in COPD
Patients (Predicted Results, Treatments A - C)

Table 14.2.2.9 Summary of Spirometric Functions Following Multiple Oral
YPL-001 Doses of 80 mg and 160 mg and Placebo in COPD
Patients (Percent Results, Treatments A - C)

Quality of Life

Table 14.2.2.10 Categorical Summary of Baseline Dyspnea Index (BDI) at
Check-in by Treatment Assignment of Multiple Oral YPL-001
Doses of 80 mg and 160 mg and Placebo in COPD Patients
(Treatments A - C)

Table 14.2.2.11 Categorical Summary of Transition Dyspnea Index (TDI)
Following Multiple Oral YPL-001 Doses of 80 mg and 160 mg
and Placebo in COPD Patients (Treatments A - C)

Table 14.2.2.12 Change From Baseline of Combined Focal Score (-9 – +9)
from Transition Dyspnea Index (TDI) Following Multiple Oral
YPL-001 Doses of 80 mg and 160 mg and Placebo in COPD
Patients (Treatments A - C)

Table 14.2.2.13 Categorical Summary of Cough and Mucus Production from

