Table 11-6 Summary of BAL WBC and Differential Following Multiple Oral YPL 001 Doses of 80 mg and 160 mg and Placebo in COPD Patients – Day 55 or Day 56 (% Change from Baseline)

BAL Inflammatory Cell	% Change from Baseline		
	Treatment A YPL-001 80 mg	Treatment B YPL-001 160 mg	Treatment C Placebo
WBC	XX ± XX (N=X)	XX ± XX (N=X)	XX ± XX (N=X)
Macrophage	XX ± XX (N=X)	XX ± XX (N=X)	XX ± XX (N=X)
Lymphocyte	XX ± XX (N=X)	XX ± XX (N=X)	XX ± XX (N=X)
Neutrophil	XX ± XX (N=X)	XX ± XX (N=X)	XX ± XX (N=X)
Eosinophil	XX ± XX (N=X)	XX ± XX (N=X)	XX ± XX (N=X)

Presented as arithmetic mean ± SD, baseline is at Check-in.
 WBC = White blood cell

Treatment A: Multiple oral doses of YPL-001 80 mg BID on Days 1 – 55
 Treatment B: Multiple oral doses of YPL-001 160 mg BID on Days 1 – 55
 Treatment C: Multiple oral doses of placebo BID on Days 1 – 55
 Note: Patients following up to Amendment version 5 of the protocol also received a morning dose on Day 56.

Source: Table 14.2.2.1

Table 11-7 Summary of BAL Inflammatory Marker Concentration Changes Following Multiple Oral YPL 001 Doses of 80 mg and 160 mg and Placebo in COPD Patients –Day 55 or Day 56 (% Change from Baseline)

BAL Inflammatory Biomarkers	% Change from Baseline		
	Treatment A YPL-001 80 mg	Treatment B YPL-001 160 mg	Treatment C Placebo
TNF- α	XXX \pm XXX (N=X)	XXX \pm XXX (N=X)	XXX \pm XXX (N=X)
IL-1 β	XXX \pm XXX (N=X)	XXX \pm XXX (N=X)	XXX \pm XXX (N=X)
IL-4	XXX \pm XXX (N=X)	XXX \pm XXX (N=X)	XXX \pm XXX (N=X)
IL-5	XXX \pm XXX (N=X)	XXX \pm XXX (N=X)	XXX \pm XXX (N=X)
IL-6	XXX \pm XXX (N=X)	XXX \pm XXX (N=X)	XXX \pm XXX (N=X)
IL-8	XXX \pm XXX (N=X)	XXX \pm XXX (N=X)	XXX \pm XXX (N=X)
IL-13	XXX \pm XXX (N=X)	XXX \pm XXX (N=X)	XXX \pm XXX (N=X)
MPO	XXX \pm XXX (N=X)	XXX \pm XXX (N=X)	XXX \pm XXX (N=X)
Neutrophil Elastase	XXX \pm XXX (N=X)	XXX \pm XXX (N=X)	XXX \pm XXX (N=X)
MCP-1	XXX \pm XXX (N=X)	XXX \pm XXX (N=X)	XXX \pm XXX (N=X)
MMP-9	XXX \pm XXX (N=X)	XXX \pm XXX (N=X)	XXX \pm XXX (N=X)

Presented as arithmetic mean \pm SD, baseline is at Check-in.

Treatment A: Multiple oral doses of YPL-001 80 mg BID on Days 1 – 55
 Treatment B: Multiple oral doses of YPL-001 160 mg BID on Days 1 – 55
 Treatment C: Multiple oral doses of placebo BID on Days 1 – 55
 Note: Patients following up to Amendment version 5 of the protocol also received a morning dose on Day 56.

Source: Table 14.2.2.3

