Note: Patients following up to Amendment version 5 of the protocol also received a morning dose on Day 56.

Program : /AAXXXX/ECR/sas_prg/stsas/tab/PROGRAMNAME.sas DDMMYYYY HH:MM

Pharmacodynamics

Inflammatory Cell Counts in BAL and Blood

Note: Tables 14.2.2.1 and 14.2.2.4 will be in a similar format:

Page X of X

Table 14.2.2.1 Summary of BAL WBC Counts Following Multiple Oral YPL-001 Doses of 80 mg and 160 mg and Placebo in COPD Patients (Treatments A - C) (Raw, % Change from Baseline, and % of WBC)

Measurement	Time Point	Statistic	Raw			% Change from Baseline			% of WBC		
			Treatment			Treatment			Treatment		
			A	B	C	A	B	C	A	B	C
WBC (units)	<Check-in>	N	X	X	X	X	X	X	NA	NA	NA
		Mean	X.XXX	X.XXX	X.XXX	X.XXX	X.XXX	X.XXX	NA	NA	NA
		SD	X.XXX	X.XXX	X.XXX	X.XXX	X.XXX	X.XXX	NA	NA	NA
		CV%	X.XXX	X.XXX	X.XXX	X.XXX	X.XXX	X.XXX	NA	NA	NA
		Median	X.XXX	X.XXX	X.XXX	X.XXX	X.XXX	X.XXX	NA	NA	NA
		Minimum	X.XX	X.XX	X.XX	X.XX	X.XX	X.XX	NA	NA	NA
		Maximum	X.XX	X.XX	X.XX	X.XX	X.XX	X.XX	NA	NA	NA
<Cell type> (units)	<Day 55 or 56>	N	X	X	X	X	X	X	X	X	X
		Mean	X.XXX	X.XXX	X.XXX	X.XXX	X.XXX	X.XXX	X.XXX	X.XXX	X.XXX
		SD	X.XXX	X.XXX	X.XXX	X.XXX	X.XXX	X.XXX	X.XXX	X.XXX	X.XXX
		CV%	X.XXX	X.XXX	X.XXX	X.XXX	X.XXX	X.XXX	X.XXX	X.XXX	X.XXX
		Median	X.XXX	X.XXX	X.XXX	X.XXX	X.XXX	X.XXX	X.XXX	X.XXX	X.XXX
		Minimum	X.XX	X.XX	X.XX	X.XX	X.XX	X.XX	X.XX	X.XX	X.XX
		Maximum	X.XX	X.XX	X.XX	X.XX	X.XX	X.XX	X.XX	X.XX	X.XX

Treatment A: Multiple oral doses of YPL-001 80 mg BID on Days 1 - 55

Treatment B: Multiple oral doses of YPL-001 160 mg BID on Days 1 - 55

Treatment C: Multiple oral doses of placebo BID on Days 1 - 55

Note: Patients following up to Amendment version 5 of the protocol also received a morning dose on Day 56.

NA = Not applicable

. = Value missing or not reportable

Programmers note: For the list of time point refer to Section 7.1.1.1 and 7.1.1.2

Differential cells include macropages, lymphocytes, neutrophils, and eosinophils

Program: /CAXXXX/XXX/sas_prg/stsas/lis_PROGRAMNAME.sas DDMMYYYY HH:MM

Inflammatory Markers in BAL and Blood

Note: Tables 14.2.2.2 and 14.2.2.5 and will be in a similar format:

Page X of X

Table 14.2.2.5 Summary of Blood Inflammatory Marker Concentrations Following Multiple Oral YPL 001 Doses of 80 mg and 160 mg and Placebo in COPD Patients (Treatments A - C)

Measurement	Time Point	Statistic	Treatment		
			A	B	C
IL-X (units)	<Screen, Day X predose> (Baseline)	N	X	X	X
		Mean	X.XXX	X.XXX	X.XXX
		SD	X.XXXX	X.XXXX	X.XXXX
		CV%	X.XXXX	X.XXXX	X.XXXX

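### For BAL cell differentials, % change from baseline is the only planned change measure; it is undefined at a zero baseline count, and its mean can differ from zero without any drug effect.

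*SAP*

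**What the plan says.** Section 7.1.1.1 covers the WBC count and four cell types, eosinophils among them. Results are to be given as "raw counts and % change from baseline and as a percent (%) of WBC for each differential". The differential comes from "microscopic examination with manual differential WBC count" at the local sites; the number of cells counted is not given. There is one lavage before and one at the end of treatment: "BAL samples for PD assessments of biomarkers will be collected at baseline at Check-in and on Day 55 or 56 of the Treatment Period". The baseline is the patient's own Check-in value.

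Section 7.1.2 calls for descriptive statistics "for the actual values (raw) and relative values (% change from baseline or total) as specified above for each type of biomarker variable" and contains no rule for a zero denominator. The SAP's rules for zeros (Section 8.5.1) concern plasma drug concentrations only.

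Three displays matter:

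- **Table 11-6 (in-text):** rows for WBC, macrophages, lymphocytes, neutrophils and eosinophils; % change only, each cell with its own N. Footnote: "Presented as arithmetic mean ± SD, baseline is at Check-in".
- **Table 14.2.2.1 (post-text, the source of Table 11-6):** "Raw, % Change from Baseline, and % of WBC". It has no absolute-change column. A dot stands for "Value missing or not reportable".
- **Tables 14.2.2.3 and 14.2.2.6 (soluble markers in BAL and blood):** the shared shell has both an absolute-change and a %-change column.

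**The concern.** A manual differential counts a limited number of cells, so a rare type can come out as exactly zero. Percent change divides by that baseline. At zero it does not exist, and at one or two counted cells a shift of a single cell moves it by 100 or 50 percentage points. The SAP anticipates below-limit plasma troughs and pre-specifies how to treat them, but it says nothing for BAL cells.

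The patients who lose their value are those with the lowest baselines, who can only stay at zero or rise. The patients who remain were selected for having at least one cell counted. The eosinophil row of Table 11-6 then describes a baseline-selected subset, and its mean need not be zero when nothing has happened. Comparing BAL inflammatory cells, eosinophils included, with placebo is a stated exploratory objective (Section 2.1), and Table 11-6 is the BAL cell table in the body of the report.

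**Working it through.** The SAP states no figure for this endpoint, so there is nothing to reproduce. The check asks how often the measure is undefined and what its mean is when there is no true change.

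**Input from the SAP.** 20 patients per arm (Section 3).

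**Assumptions, not in the SAP.** k = 200 to 500 cells counted per slide; mean eosinophil fraction p = 0.2% to 2%; patient fractions follow a gamma distribution with CV 100%; total WBC is unchanged; no true change between the two lavages.

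**Formulas.** Let m = k × p be the mean number of eosinophils counted. Treating the count as Poisson around each patient's own mean:

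- Chance of a zero baseline: P0 = 1/(1 + m).
- Expected patients with a defined value: 20 × (1 - P0).
- Given a baseline count x, the expected follow-up count is (1 + x) × m/(1 + m). Averaging the ratio to x over x > 0 gives mean % change in those kept = 100 × P0 × [ln(1 + m) - 1].

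Example, k = 200 and p = 0.2%: m = 0.4; P0 = 1/1.4 = 0.714; mean = 100 × 0.714 × (0.336 - 1) = -47.4%.

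The last two columns come from a binomial simulation with 2,000,000 patients per setting.

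| Cells | Mean fraction | m | Zero baseline | Defined, of 20 | Mean % change, formula | Mean, simulated | SD, simulated |
|---|---|---|---|---|---|---|---|
| 200 | 0.2% | 0.4 | 71% | 5.7 | -47.4 | -47.3 | 77 |
| 300 | 0.2% | 0.6 | 62.5% | 7.5 | -33.1 | -33.0 | 88 |
| 300 | 0.5% | 1.5 | 40% | 12.0 | -3.3 | -3.4 | 104 |
| 300 | 1% | 3 | 25% | 15.0 | +9.7 | +9.4 | 104 |
| 300 | 2% | 6 | 14% | 17.1 | +13.5 | +13.3 | 94 |
| 500 | 2% | 10 | 9% | 18.2 | +12.7 | +12.6 | 84 |

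**Sign.** The formula is zero when ln(1 + m) = 1, that is m = 1.72 cells. Below that the null mean is negative, above it positive.

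**Instability.** At 300 cells and 0.5%, the standard error of an arm's mean is about 104/√12 = 30 percentage points.

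**Absolute change, same simulation.** At 300 cells and 0.2%, the mean change is -0.62 cells in those kept and +0.38 in those dropped. Over everyone it is 0.625 × 0.375 - 0.375 × 0.621, which is 0.00. It is about zero in every setting.

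**Without between-patient variation.** P0 = (1 - p)^k. This gives 67% (200 cells, 0.2%), 22% (300 cells, 0.5%) and 0.2% (300 cells, 2%). The null mean % change at Poisson mean counts of 0.6, 1, 2 and 4 is -49%, -23%, +16% and +32%. The pattern is the same, but the loss can be close to nil.

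**The case against.** The strongest reply is that little is lost. Three scales are planned, and a patient with no eosinophils at Check-in still appears in the raw and % of WBC columns of Table 14.2.2.1. Every cell of Table 11-6 prints its N, so a shortfall would be visible. Section 12.1 lets the content of in-text pharmacodynamic tables be modified in light of the data. The endpoint is exploratory and descriptive, and the Table 14.2.2.1 shell has no p-value rows.

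All of that stands, and it limits the point. It does not remove it: the raw columns summarize each visit separately, no BAL figure is planned, and the only change result is the one that fails at zero. A printed N shows that patients are missing, but not that they are missing because of their baseline.

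Three stronger readings are tempting, and the documents do not support them:

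- **That these patients leave the analysis.** They leave the % change result only.
- **That rare cells would seem to fall in every arm.** Under the assumptions above, the mean that Table 11-6 reports falls only when the expected count is below about 1.7 cells; above that it rises.
- **That the comparison with placebo is biased.** The Check-in lavage (Day -3 to -1) precedes randomization on Day 1 (Section 3), so this selection does not by itself favour an arm.

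**Conclusion.** The point holds in a limited form. For BAL differentials the plan relies on a single change measure that is undefined at a zero baseline, gives no rule for that case, and shows only its mean and SD in the text of the report. The eosinophil row is the one chiefly exposed. With CV 100%, 200 to 500 cells and mean fractions of 0.2% to 2%, between 71% and 9% of patients would have no value, leaving about 6 to 18 of 20 per arm. The mean % change with no effect would lie between about -47% and +13%, in the same direction in each arm.

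These sizes rest wholly on assumed cell counts, fractions and between-patient variation. With common eosinophils and little variation between patients, almost nobody would be lost. What does not depend on the assumptions is that the measure has no value at zero and that an absolute change, already planned for the soluble markers, is absent for the cells. The safety endpoint and the symptom endpoints are not touched.

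**What to change.** - **Tables 11-6 and 14.2.2.1:** add absolute change from Check-in, in cells/mL and in percentage points of WBC, with median and range, for all patients with paired samples. Tables 14.2.2.3 and 14.2.2.6 already carry an absolute-change column for the soluble markers.
- **Sections 7.1.1.1 and 7.1.2:** state that % change is not calculated when the baseline count is zero, and that the number of such patients is reported by arm and cell type.
- **Eosinophils:** keep % change as a supportive result only, shown with its N.

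No new data are needed, since the values are already collected and listed by patient. The cost is a sentence or two in the SAP and one or two extra table columns.

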7.1.1.2 Biomarkers in Blood

Blood samples for PD assessments of biomarkers will be collected in pre-chilled evacuated tubes containing K₂EDTA at screening, on Days 1 and 54 (± 1) or Day 56 of the Treatment Period prior to dosing (predose) and at 1 hour postdose. In addition, predose samples will be collected on Days 15 (± 2), 29 (± 2), and 43 (± 2) of the Treatment Period.

Biomarker assessments include:

- WBC counts and differential (including monocytes, lymphocytes, neutrophils, and eosinophils) will be expressed as raw counts, % change from baseline, and as % of WBC for each differential.

WBC and differential counts in blood will be determined using a differential stain (blood smear; microscopic examination with manual differential WBC count) at the local Investigator sites.

- Concentrations of CRP, fibrinogen, TNF- α , IL-1 β , IL-4, IL-5, IL-6, IL-8, IL-13, MCP-1, and MMP-9 will be expressed as raw and % change from baseline levels. Baseline is defined as the predose time point at Check-in of the Treatment Period level and is patient specific.

The concentrations of MMP-9 will be determined using an ELISA assay and the rest of blood inflammatory markers will be determined using Luminex® assays. All assays are validated with respect to accuracy, precision, linearity, sensitivity,

and specificity at Temple University School of Medicine (Philadelphia, Pennsylvania, USA).

7.1.1.3 Pulmonary Function Biomarkers

Spirometry measures for assessment of the pulmonary function will be taken pre- and post-bronchodilator (albuterol) administration at Screening (baseline), at Check-in, on Days 15 (± 2), 29 (± 2), 43 (± 2), and 55 or 56 (predose) of the Treatment Period, and prior to early termination, if applicable.

Pulmonary function measurements include the following parameters below:

- FEV1;
- FVC;
- FEV1/FVC;
- IC.

Short and long acting β 2-agonist and anticholinergic bronchodilators agents will be withheld approximately 4 and 24 hours, respectively, before each pre-bronchodilator spirometry.

At screening, baseline pre-bronchodilator spirometry will be performed (prior to albuterol administration) for a minimum of 3 times and a maximum of 8 times in order to obtain 3 manoeuvres with FEV1 values within 150 mL of each other, using the manoeuvre with the highest value of FEV1 and FVC as the basis for comparison.

Patients shall receive 4 inhalations of albuterol, (100 μ g/inhalation), for a total dose of 400 μ g via metered-dose inhaler using a spacer. Within approximately 20 to 30 minutes after albuterol administration, the baseline post-bronchodilator spirometry will be performed.

Assessment of FEV1 stability will take place:

1. Prior to Day 1 dosing of the Treatment Period (Check-in measurement): Predose FEV1 is defined as the time-point prior to Day 1 dosing in the Treatment Period and will be performed pre- and post-bronchodilator administration. Predose FEV1 will be compared to the corresponding baseline measurement. If the best FEV1 measurement at predose at Check-in of the Treatment Period has declined by greater than 20% from the best FEV1 at screening, the visit may be rescheduled up to 3 times, at the discretion of the Investigator.
2. Following Day 1 dosing: At all other spirometry time point, measurements will be performed once. If the value shows a difference of greater than 150 mL

decline than the best FEV1 value collected predose at Check-in, up to 3 measures will be performed.

Consideration should be given, if a patient experiences any change in post Day 1 dose FEV1 from the Day 1 predose FEV1 value (measured following dosing with albuterol) equal to or greater than 20 % and should alert the PI to consider whether individual patients should continue to dose.

7.1.1.4 Quality of Life Assessments

Baseline Dyspnea Index/Transition Dyspnea Index (BDI/TDI):

BDI/TDI has 3 domains (functional impairment, magnitude of task and magnitude of effort) with the values added for a combined focal score.

Dyspnea will be assessed at Check-in of the Treatment Period (considered as the baseline) using the BDI score. The BDI scores range from 0 (very severe impairment) to 4 (no impairment) for each domain with the baseline focal score consisting of the sum of each domain (0 to 12).

Dyspnea throughout the study will be assessed at predose on Days 15 (± 2), 29 (± 2), 43 (± 2), and 54 (± 1) or Day 56 of the Treatment Period using the TDI score. The change from baseline (BDI score) is measured by the TDI score which ranges from -3 (major deterioration) to +3 (major improvement) for each domain with the TDI focal score consisting in the sum of each domain (-9 to +9).

COPD Assessment Test (CAT):

Overall impact of a patient's condition (i.e., COPD) on their life will be assessed. The CAT questionnaire will be completed by patients at Check-in of the Treatment Period, and at predose on Days 15 (± 2), 29 (± 2), 43 (± 2), 54 (± 1) or Day 56. CAT score range from 0 (no impact on daily activities) to 40 (very high impact on daily activity).

7.1.2 Data Summarization and Presentation

Descriptive statistics will be generated using SAS[®] Version 9.3 (or higher) for the actual values (raw) and relative values (% change from baseline or total) as specified above for each type of biomarker variable. When applicable, the PD biomarkers (BAL, blood, pulmonary function) will be summarized by treatment group and time point using descriptive statistics including sample size (N), arithmetic mean, standard deviation (SD), coefficient of variation (CV%), median, minimum, and maximum.

Figures will be created to display mean measure, level or activity value as a function of time on linear plots with and without SD, as appropriate.

The quality of life parameters reported from the BDI/TDI and CAT questionnaires will be listed and presented descriptively using SAS® Version 9.3 (or higher)

Additional analysis may be performed if deemed appropriate.

